I confirm that I have read the above protocol in the latest version. I understand it, and I will work according to the principles of Good Clinical Practice (GCP) as described in the United States Code of Federal Regulations (CFR) – 45 CFR part 46 and 21 CFR parts 50, 56, and 312, and in the International Conference on Harmonization (ICH) document Guidance for Industry: E6 Good Clinical Practice: Consolidated Guidance dated April 1996. Further, I will conduct the study in keeping with local legal and regulatory requirements.	
As the site Principal Investigator, I agree to carry out the study by the criteria written in the protocol and understand that no changes can be made to this protocol without the written permission of the IRB and NIAID.	
<hr/> Site Principal Investigator (Print)	
<hr/> Site Principal Investigator (Signature)	<hr/> Date

Protocol Synopsis

Title	Treg Adoptive Therapy in Subclinical Inflammation in Kidney Transplantation (TASK)
Short Title	Tregs in Subclinical Inflammation
Clinicaltrials.gov Identifier	NCT02711826
Clinical Phase	Phase I/ II
Number of Sites	Cleveland Clinic Northwestern University University of Alabama at Birmingham University of California at San Francisco University of Colorado University of Michigan
IND Sponsor/Number	NIH/NIAID/DAIT/ #16626
Primary Safety Objective	This study will evaluate the safety of polyTregs in adult kidney transplant recipients.
Secondary Safety Objective	Participants receiving polyTregs will be evaluated for the safety of converting from CNI-based maintenance therapy to mTOR inhibitors after Treg therapy.
Primary Efficacy Objective	This study will evaluate whether polyclonally expanded Tregs (polyTregs) reduce graft inflammation relative to their enrollment biopsy compared to those receiving CNI-based maintenance therapy with similar baseline biopsy findings.
Secondary Efficacy Objective	This study will evaluate whether polyTregs can reduce graft inflammation by 25% or more in the 2 weeks after polyTreg infusion relative to the enrollment biopsy.
Mechanistic Objectives	This study will evaluate the impact of polyTregs on the immunological profiles of kidney transplant recipients.

Study Design	
Multi-center, open-label, randomized, controlled trial with 2 cohorts:
 
 1. Maintenance CNI based immunosuppression therapy 2. polyTregs 
The original study design included a third treatment arm (donor alloantigen reactive Tregs or darTregs). One subject was treated with darTregs prior to protocol version 9.0 in which this treatment arm was eliminated due to excessive manufacturing failures.

Primary Safety Endpoints	
The safety of polyTregs (Group 2) will be described in comparison with CNI-based maintenance IS therapy (Group 1) by:
 
 1. The timing and incidence of Banff 2A or higher acute cell-mediated rejection and/or acute antibody mediated rejection 2. The timing and incidence of study defined Grade 3 or higher infection
Secondary Safety Endpoints for polyTregs	
The safety of PolyTregs will also be described in Groups 1 and 2 by:
 
 1. Timing, incidence, and severity of polyTreg infusion reactions 2. Timing, incidence, and severity of culture-proven and clinically diagnosed infections after polyTreg infusion 3. Timing, incidence, and severity of acute rejection using Banff grading 4. Timing and incidence of BK viremia and CMV reactivation 5. Timing and incidence of > 10% decrease in eGFR compared to baseline
Secondary Safety Endpoint for mTOR Therapy	
The safety of mTOR therapy after Treg infusion will be assessed by the incidence and timing of acute rejection. Subjects who receive Tregs and convert to mTOR therapy will be compared to subjects who did not convert to mTOR therapy, as well as subjects in Group 1.

Primary Efficacy Endpoint	
The primary efficacy endpoint will be the change in inflammation as measured by the percentage area of cortex occupied by inflammatory cells using computer-assisted quantitative image analysis on the biopsy 7 months after group allocation, expressed as the percent change relative to the baseline biopsy.

Secondary Efficacy Endpoints	The secondary efficacy endpoint will be the proportion of subjects exhibiting a relative decrease of 25% or more inflammation between the baseline kidney biopsy and the biopsy 2 weeks after polyTregs, measured as the percentage area of cortex occupied by inflammatory cells using computer-assisted quantitative image analysis. Additional secondary efficacy endpoints are the number of subjects who exhibit a relative decrease of 50% or more inflammation on kidney biopsy at 2 weeks after polyTregs; and the proportion of subjects who exhibit a relative decrease of 25% or more inflammation at 7 months after group allocation.
Primary Mechanistic Endpoint	The primary mechanistic endpoints are the immunologic profiles of kidney transplant recipients using graft CRM (common response module) gene expression of rejection and/or evidence of inflammation in biopsies at 2 weeks after infusion (Group 2) and 7 months after group allocation (Groups 1 and 2).
Secondary Mechanistic Endpoints	The secondary mechanistic endpoints are the immunologic profiles of kidney transplant recipients using: 
 1. Persistence of infused Tregs in blood and biopsies using deuterium labeling and T cell repertoire analysis (Group 2) 2. Cytokine and CRM (common response module) mRNA and protein profiles in the urine as correlates of acute rejection and/or histologic evidence of inflammation and graft fibrosis (Groups 1 and 2) 3. Peripheral blood kSORT (kidney solid organ response test) mRNA expression of rejection/increased immune response (Groups 1 and 2)
Accrual Objective	14 Subjects Total: 7 subjects on CNI maintenance therapy 7 subjects to receive polyTregs
Study Duration	6.5 Year Accrual, 12 Months Follow Up
Treatment Description	Subjects will be on maintenance IS therapy using CNI + MMF/MPA with or without steroids at the time of study entry. Eligible subjects will be randomized to receive: 
 1. Standard CNI maintenance IS (no Tregs) 2. $550 \pm 450 \times 10^6$ polyTregs After receiving at least 300×10^6 polyTregs infusion, eligible subjects will start mTOR inhibitor.

Inclusion Criteria	
Individuals who meet all of the following criteria are eligible for enrollment as study participants:
 
1. Subject must be able to understand and provide informed consent2. Age ≥ 18 years of age at the time of study entry3. Recipients of non-HLA identical living or deceased donor renal transplants4. Protocol renal allograft biopsy at 5 months (± 8 weeks) after transplantation with Banff i1 and/or ti1 with concomitant t scores t0, t1, t2 or t3; Banff i2 and/or ti2 with concomitant t scores t0 or t1; and without v > 0, [ptc + g] ≥ 2, C4d > 1 (by IF), or C4d > 0 (by IHC) confirmed by central pathologist. Subjects must not be treated for pathologic criteria (e.g., steroids).5. eGFR ≥ 30 ml/min at the time of study entry6. Maintenance immunosuppression consisting of tacrolimus, MMF/MPA \pm prednisone (≤ 10 mg/day)7. Current immunizations including TdAP, pneumococcal and seasonal influenza vaccines prior to study treatment, completed prior to randomization and no less than 14 days prior to planned manufacturing collection8. Hepatitis B serologies must be:
a. Positive HB surface antibody, negative HB core antibody and negative HB surface antigen for recipients immune to hepatitis Bb. Negative HB surface antibody, negative HB core antibody and negative HB surface antigen for non-immune/ HBV naïve recipients provided donor had negative HB core antibody and negative HB surface antigen at the time of donation9. Negative TB test (PPD, interferon-gamma release assay, ELISPOT testing) within 1 year prior to enrollment. Subjects with a history of TB (positive TB test without active infection) must have completed one of the latent TB infection treatment regimens endorsed by the CDC (Division of TB Elimination, 2016). Alternative regimens for latent TB infection eradication will be adjudicated by the site's infectious disease specialist.10. Female subjects with childbearing potential must have reviewed Mycophenolate REMS and have a negative pregnancy test upon study entry.11. Female subjects with childbearing potential must agree to use FDA approved methods of birth control for the duration of the study; subjects must consult with their physician and determine the most suitable method(s) that are greater than 80% effective (http://www.fda.gov/birthcontrol)
--------------------	-------------------------------------------------------------------------------------------------------------------------------------------------------------------------------------------------------------------------------------------------------------------------------------------------------------------------------------------------------------------------------------------------------------------------------------------------------------------------------------------------------------------------------------------------------------------------------------------------------------------------------------------------------------------------------------------------------------------------------------------------------------------------------------------------------------------------------------------------------------------------------------------------------------------------------------------------------------------------------------------------------------------------------------------------------------------------------------------------------------------------------------------------------------------------------------------------------------------------------------------------------------------------------------------------------------------------------------------------------------------------------------------------------------------------------------------------------------------------------------------------------------------------------------------------------------------------------------------------------------------------------------------------------------------------------------------------------------------------------------------------------------------------------------------------------------------------------------------------------------------------------------------------------------------------------------------------------------------------------------------------------------------------------------------------------------------------------------------------------------------------------------------------------------------------------------------------------------------------------------------------------------------------------------------------------------------------------------------------------------------------------------------------------------------------------------------------------------------------------------------------------------------------------------------------------------------------------------------------------------------------------------------------------------------------------------------------------------------------------------------------------------

Exclusion Criteria	
Individuals who meet any of these criteria are not eligible for enrollment as study participants:
 
1. Inability or unwillingness of a participant to give written informed consent or comply with study protocol2. History of malignancy; except adequately treated basal cell carcinoma3. History of graft loss from acute rejection within 1 year after any previous transplant4. History of transplant renal artery stenosis5. History of cellular rejection prior to enrollment that did not respond to steroids and/or subsequent creatinine after treatment for rejection greater than 15% above baseline6. Known hypersensitivity to mTOR inhibitors or contraindication to everolimus (such as history of wound healing complications)7. Any chronic illness requiring uninterrupted anti-coagulation after kidney transplantation8. Post-transplant DSA >5000 MFI or post-transplant treatment with IVIg for DSA. Enrolled subjects with post-transplant DSA >2000 MFI will not be eligible for mTOR conversion.9. Positive HIV 1 or HIV 2 serology prior to transplantation10. Known positive HBSAg, or HBcAb serology11. Proteinuria with urine pr/cr > 1.0 g/g12. Any condition requiring chronic use of corticosteroids >10mg/day at the time of study entry13. Subjects requiring treatment for pathologic findings on study eligibility biopsy (see inclusion 4).14. Active infection at the time of study entry15. History of active TB or latent TB without adequate treatment (see inclusion 10).16. Serum BK virus >1,000 copies/ml by PCR at the time of study entry17. Hematocrit <27%; ANC < 1,000/μL; lymphocytes <500/μL; at the time of study entry18. Participation in any other studies with investigational drugs or regimens in the preceding year19. Any condition or prior treatment which, in the opinion of the investigator, precludes study participation20. Unable to provide adequate biopsy specimen (paraffin embedded formalin fixed) from eligibility biopsy (3-7 months post-transplant) for quantitative analysis.21. EBV naïve recipient of a kidney from an EBV positive donor, historically EBV naïve recipient with primary EBV infection at the time of screening (primary anti-VCA IgM, without antibody to EBNA), positive EBV PCR22. Hepatitis C Virus AB positive subjects with negative HCV PCR are eligible if they have spontaneously cleared infection or are in sustained virologic remission for at least 12 weeks after treatment.23. Positive SARS-CoV2 testing by RT-PCR
--------------------	---------------------------------------------------------------------------------------------------------------------------------------------------------------------------------------------------------------------------------------------------------------------------------------------------------------------------------------------------------------------------------------------------------------------------------------------------------------------------------------------------------------------------------------------------------------------------------------------------------------------------------------------------------------------------------------------------------------------------------------------------------------------------------------------------------------------------------------------------------------------------------------------------------------------------------------------------------------------------------------------------------------------------------------------------------------------------------------------------------------------------------------------------------------------------------------------------------------------------------------------------------------------------------------------------------------------------------------------------------------------------------------------------------------------------------------------------------------------------------------------------------------------------------------------------------------------------------------------------------------------------------------------------------------------------------------------------------------------------------------------------------------------------------------------------------------------------------------------------------------------------------------------------------------------------------------------------------------------------------------------------------------------------------------------------------------------------------------------------------------------------------------------------------------------------------------------------------------------------------------------------------------------------------------------------------------------------------------------------------------------------------------------------------------------------------------------------------------------------------------------------------------------------------------------------------------------------------------------------------------------------------------------------------------------------------------------------------------------------------------------------------------------------------------------------------------------------------------------------------

15. Statistical Considerations and Analytical Plan	70
15.1. Overview	70
15.2. Measures to Minimize Bias	70
15.3. Analysis Plan.....	70
15.3.1. Analysis Samples	70
15.3.2. Endpoint Assessments	70
15.3.3. Descriptive Analyses	73
15.4. Interim Analyses.....	74
15.5. Sample Size Considerations	74
16. Identification and Access to Source Data	76
16.1. Source Data	76
16.2. Access to Source Data	76
17. Protocol Deviations	77
17.1. Protocol Deviation Definitions	77
17.2. Reporting and Managing Protocol Deviations	77
18. Ethical Considerations and Compliance with Good Clinical Practice.....	78

18.1.	Statement of Compliance	78
18.2.	Informed Consent Process	78
18.3.	Privacy and Confidentiality	78
19.	Publication Policy	79
20.	References	80
	Appendix 1. Donor Assessments	86
	Appendix 2. Group 1 Recipient Schedule of Events	87
	Appendix 3. Group 2 Recipient Schedule of Events	88
	Appendix 4. Manufacturing Timeline	89

Glossary of Abbreviations

CFR	Code of Federal Regulations
COVID-19	Coronavirus Disease 2019
CRF	Case Report Form
CRM	Common Response Module
CTCAE	Common Terminology Criteria for Adverse Events
DAIT	Division of Allergy, Immunology, and Transplantation
darTregs	Donor Alloantigen Reactive T Regulatory Cells
DSMB	Data Safety Monitoring Board
FDA	Food and Drug Administration
GCP	Good Clinical Practice
ICH	International Conference on Harmonization
IND	Investigational New Drug
IRB	Institutional Review Board
kSORT	Kidney Solid Organ Response Test
mTOR	Mammalian Target of Rapamycin
NIAID	National Institute of Allergy and Infectious Diseases
PI	Principal Investigator
polyTregs	Polyclonal T Regulatory Cells
Mycophenolate REMS	Mycophenolate Risk Evaluation and Mitigation Strategy
SAE	Serious Adverse Event
SAP	Statistical Analysis Plan
SAR	Suspected Adverse Reaction
SARS-CoV2	Severe Acute Respiratory Syndrome Coronavirus 2
SCI	Subclinical Inflammation
SOP	Standard Operating Procedure
SUSAR	Serious Unexpected Suspected Adverse Reaction

Study Definitions Page

Acute Cell-mediated Rejection	Banff 2007 Type 1A or higher and clinical treatment for acute rejection. Central reading will be utilized when accounting for study stopping rule and for safety endpoint.
Severe Acute Cell-mediated Rejection	Banff 2007 Type 2A or higher and clinical treatment for acute rejection. Central reading will be utilized when accounting for study stopping rule and for safety endpoint.
Antibody Mediated Rejection	Diffusely positive staining for C4d, presence of circulating anti-donor antibodies, and morphologic evidence of acute tissue injury.
Graft Inflammation	Banff i1 and/or ti1+ t0, t1, t2 or-t3 or Banff i2 and/or ti2 + t0 or t1
Graft Failure	90 consecutive days of dialysis dependency
Infection, Severe	Study defined grade 3 or higher; culture-proven and clinically diagnosed
Investigational Agent	polyTregs, everolimus
Protocol Mandated Procedures	Any procedure or specimen collection performed solely for the purpose of this research study, not considered site specific standard of care.
Randomized	A subject who met eligibility criteria, signed informed consent document, and was randomly assigned to one of two treatment groups.
Withdrawn from Study Therapy	Subjects who prematurely discontinue the study after receiving polyTregs.
Treatment for Rejection	Treatment of rejection in this protocol constitutes use of IV steroids and/or Thymoglobulin. Adjustment of maintenance immunosuppression medications will not be counted as treatment for rejection.
Women of Childbearing Potential	WOCBP includes any female who has experienced menarche and who has not undergone successful surgical sterilization (hysterectomy, bilateral tubal ligation, or bilateral oophorectomy) or is not postmenopausal (defined as amenorrhea \geq 12 consecutive months; or women on hormone replacement therapy with documented serum follicle stimulating hormone level > 35 mIU/mL). Even women who are using oral, implanted, or injectable contraceptive hormones or mechanical products such as an intrauterine device or barrier methods (diaphragm, condoms, spermicides) to prevent pregnancy or practicing abstinence or where the partner is sterile (e.g., vasectomy), should be considered to be of childbearing potential.

1. Study Hypotheses/Objectives

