3.3.2 Secondary Safety Endpoint for mTOR Therapy

The safety of mTOR therapy after Treg infusion will be assessed by the timing and incidence of acute rejection in Group 2. Subjects who receive Tregs and convert to mTOR therapy will be compared to subjects who did not convert to mTOR therapy; as well as subjects in group 1.

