6.4. Rejection after Initiation of Everolimus

Any subject with biopsy proven or treated rejection after the start of study mandated everolimus will discontinue everolimus and resume tacrolimus. Target tacrolimus trough levels will be 4-11 mcg/L.

7. Other Medications

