7.4. Treatment of Rejection

Patients who are clinically suspected to have a rejection will undergo a kidney biopsy. Biopsies will be read locally according to the Banff criteria and if acute rejection is diagnosed, it will be treated according to the current standard of care. Samples of blood, urine and kidney tissue will be obtained for mechanistic analysis prior to the treatment. Digital images of the biopsies will also be reviewed later by the central pathology core.

8. Study Mandated Procedures

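### The protocol counts a cell-mediated rejection only if it was treated with IV steroids or Thymoglobulin, so one on everolimus followed only by return to tacrolimus can drop out of the mTOR safety endpoint; the SAP's Banff-based scoring conflicts with this

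*Protocol*

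**What the plan says.** The protocol's Study Definitions Page gives acute cell-mediated rejection two conditions: "Banff 2007 Type 1A or higher and clinical treatment for acute rejection". The severe form has the same structure with a threshold of 2A. For both, "Central reading will be utilized when accounting for study stopping rule and for safety endpoint".

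The same page says what counts as treatment: "Treatment of rejection in this protocol constitutes use of IV steroids and/or Thymoglobulin". It then excludes other measures: "Adjustment of maintenance immunosuppression medications will not be counted as treatment for rejection".

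Antibody mediated rejection is defined by findings alone, with no treatment condition: "Diffusely positive staining for C4d, presence of circulating anti-donor antibodies, and morphologic evidence of acute tissue injury".

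For converted subjects, section 6.4 states: "Any subject with biopsy proven or treated rejection after the start of study mandated everolimus will discontinue everolimus and resume tacrolimus". Section 3.3.2 sets the endpoint: "The safety of mTOR therapy after Treg infusion will be assessed by the timing and incidence of acute rejection in Group 2". Converters are to be compared with non-converters and with Group 1. Table 7 lists acute rejection as the only endpoint under mTOR therapy.

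SAP section 8.1.1 defines cell-mediated rejection by Banff 2007 and scores the severe form on a grade of IIA or higher, with no mention of treatment. SAP section 8.2.1 lists acute rejection by Banff grading, and a separate row for rejection after conversion (day 69 to day 405). It does not define rejection for that row. SAP section 10, which lists changes from the protocol, does not mention the treatment condition.

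**The concern.** Section 6.4 is triggered by rejection that is either biopsy proven or treated, so the protocol itself allows for a biopsy-proven rejection that was not treated. Its mandated response is a maintenance change, which is exactly what the definitions page refuses to count. The endpoint meant to show whether conversion is safe can therefore miss a rejection that was managed by undoing the conversion.

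The comparison groups have no mandated switch of this kind, so the chance of being missed may differ between the groups compared. Group 2 has at most 7 subjects and converters are a subset, so a single event can be the whole signal. Because the protocol and SAP use different rules, two analysts could also report different counts from the same biopsies.

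**Working it through.** The documents give no expected rejection rate and no number of converters, so there is no stated figure to reproduce. The check is a comparison of texts, followed by an illustration of scale.

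**Step 1: apply each definition to the same case.** The grades below are central readings of Banff 1A or higher, except in the last row.

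| Case | Protocol definitions page | SAP, read as Banff grade alone |
|---|---|---|
| Converter, given IV steroids or Thymoglobulin | counted | counted |
| Converter, returned to tacrolimus only | not counted | counted |
| Converter, given another agent only (e.g. oral steroids) | not counted | counted |
| Group 1 or non-converter, maintenance change only | not counted | counted |
| Any subject meeting the antibody mediated definition | counted | counted |

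The SAP column is a reading for the mTOR row, because section 8.2.1 leaves rejection undefined there. SAP section 3 refers its safety objective to a study definitions page, but the SAP's table of contents lists none. If the protocol's page is meant, the treatment condition returns by that route.

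**Step 2: does section 7.4 close the gap?** It says that "if acute rejection is diagnosed, it will be treated according to the current standard of care". Three points leave the gap open:

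1. Section 7.4 concerns patients clinically suspected of rejection. Section 8.3 describes the month-7 biopsy as surveillance.
2. Treatment follows the local reading and central review comes later, while the endpoint uses the central reading. A central 1A that was read lower locally could go untreated and so uncounted.
3. Standard of care names no agents, so it is not confined to the two that count.

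**Step 3: scale, under an assumption.** Let n be the number of converters, assumed to be between 2 and 7 (Group 2 has 7 subjects). One uncounted event changes the incidence from 1/n to 0/n, a fall of 100/n percentage points. Table 7 names exact binomial limits:

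- 0/n: upper limit = 1 − 0.025^(1/n). For n = 3: 1 − 0.025^(1/3) = 70.8%.
- 1/n: lower limit = 1 − 0.975^(1/n); upper limit = the 97.5% point of Beta(2, n − 1).

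| n (assumed) | Event counted (95% CI) | Event not counted (95% CI) | Fall (points) |
|---|---|---|---|
| 2 | 50.0% (1.3–98.7) | 0% (0–84.2) | 50.0 |
| 3 | 33.3% (0.8–90.6) | 0% (0–70.8) | 33.3 |
| 5 | 20.0% (0.5–71.6) | 0% (0–52.2) | 20.0 |
| 7 | 14.3% (0.4–57.9) | 0% (0–41.0) | 14.3 |

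For acute rejection in Group 2 as a whole, one uncounted event is 1/7 = 14.3 points.

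**The case against.** A reader might infer that rejections on everolimus simply disappear and that the bias favours the everolimus and polyTreg arm. The documents do not support that, for these reasons:

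- **The loss is conditional.** Section 6.4 does not offer the switch as a substitute for treatment, and section 7.4 calls for treatment of diagnosed rejection. The event is lost only if neither IV steroids nor Thymoglobulin is given. In the protocol's own serial-biopsy cohort (section 2.1.2.1), treatment for subclinical rejection included methylprednisolone pulse, Thymoglobulin and IVIg.
- **The direction is open.** The maintenance exclusion applies to every group, so a Group 1 rejection managed by a tacrolimus change is also uncounted. A mandated switch does not show that converters receive IV treatment less often.
- **The SAP does not repeat the condition.** Read alone, it would count the event.
- **The data survive.** Biopsy-proven rejection is reportable within 24 hours whether or not treated (section 14.2.4), and the one-year and for-cause biopsies are centrally read (section 8.3).
- **The endpoint is secondary and descriptive.** With 0/3 the upper limit is still 70.8%, so even a correct zero could not establish safety.

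A reader might also take about 3 of 7 as the number of converters, since persistent inflammation in 56.5% of that cohort leaves 43.5%, and 0.435 × 7 ≈ 3. That is a poor proxy. Those 23 recipients had conventional treatment and a biopsy six months later. Conversion needs resolution two weeks after infusion, at least 300 × 10^6 cells and no DSA above 2000 MFI.

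All of this limits the claim. It does not remove the gap in the protocol definition or the conflict with the SAP, and an adverse event listing does not correct a prespecified endpoint comparison.

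**Conclusion.** The point holds as a definitional gap together with a conflict between the two documents. Under the protocol, a centrally read cell-mediated rejection in a converter who receives neither IV steroids nor Thymoglobulin is not an event in the acute-rejection endpoint or the sole mTOR safety endpoint. Under the SAP's Banff-based wording it would be, and SAP section 10 does not record the difference. The same unrecorded difference affects severe cell-mediated rejection in the primary safety endpoint.

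The undercount may be differential, but neither its direction nor its size can be established from the documents. The fall of 50.0 to 14.3 percentage points rests on an assumed 2 to 7 converters and one hypothetical event. It shows sensitivity to a single event and is not an estimate of bias.

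**What to change.** Reconcile the Study Definitions Page, protocol section 6.4 and SAP sections 8.1.1 and 8.2.1, so that one definition of rejection governs each endpoint.

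- For the secondary acute-rejection and mTOR endpoints, count every centrally read Banff 1A or higher on a for-cause or month-7 biopsy regardless of management, identically in all groups.
- Show the subset treated with IV steroids or Thymoglobulin as a second line.
- State this definition for the mTOR row in SAP section 8.2.1 and list the change in SAP section 10.
- Do not count the everolimus-to-tacrolimus switch itself as treatment. That would give converters alone an extra route to an event and create the opposite asymmetry.

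The cost is wording; the central readings are already planned. The small downside is that some mild, untreated rejections will be counted in all groups. The change concerns event counting only and leaves clinical management as it is.
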